1. INTRODUCTION AND STUDY SYNOPSIS

The Heart OMics in AGing (HOMAGE) randomised controlled trial (RCT) is a Phase II proof of concept clinical trial within the EU FP 7 HOMAGE programme, with the aim of bioprofiling response to mineralocorticoid receptor antagonists for the prevention of heart failure.

1.2 Study rationale and hypothesis

Despite advances in care, prognosis remains poor once overt heart failure (HF) has developed. Therefore, prevention is an important frontier in HF management. Prevention is most efficient when directed toward patients at risk and when mechanistically targeted to those most likely to respond. An increase in myocardial and possibly vascular collagen content may be a major determinant of the transition to HF. In patients with hypertension and diabetes, two important risk-factors for HF, changes in blood markers of fibrosis occur before clinically overt HF develops. These markers are also related to prognosis.

We hypothesize that the mineralocorticoid receptor antagonist (MRA), spironolactone, may prevent HF by acting on extracellular matrix remodelling, especially in patients with active

fibrogenesis, identified by high Gal-3 levels. The benefit/risk ratio of spironolactone might be superior in patients with a higher compared to lower plasma concentrations of Gal-3.

1.3 Study design and population

The study follows a prospective randomized open label blinded evaluation (PROBE) parallel group design. All persons evaluating key tests, the clinical endpoints committee, and those conducting laboratory biomarkers tests will be kept blind to the treatment allocation.

The study will be conducted in approximately 800 patients at increased risk of developing heart failure in approximately 9 centers in the United Kingdom, France, Italy, Ireland, Germany and the Netherlands. Patients will be screened in primary and secondary care. Each center will have its own recruitment strategies under review of local ethics committees.

Inclusion criteria are as follows:

1. Written informed consent obtained prior to the initiation of any study procedures;
2. Age >60 years
3. Clinical risk factors, Either;
 - Coronary artery disease (MI, angioplasty or CABG)

Or at least two of the following;

 - Diabetes Mellitus requiring hypoglycaemic pharmacotherapy
 - Pharmacological treatment for hypertension
 - Microalbuminuria (defined as creatinine > 30mg/g or 3mg/mmol)
 - Abnormal ECG (LVH, QRS >120msec, pathological Q-waves)
4. Biological risk: NT- Pro-BNP values between 125 and 1,000 ng/L or BNP between 35 and 280pg/ml (consistent with ESC guidelines indicating risk of HF but helping to rule out prevalent HF or atrial fibrillation)

Exclusion criteria are described in full in the trial protocol.

All patients randomised before 31 December 2017 will be treated and followed up for a period of nine months. Patients randomised from 1 January 2018 until 30 June 2018 will be followed up for a period of between 3 and 6 months. The final patient visit will occur no later than 30 September 2018.

Patients randomised to the experimental group will receive spironolactone, titrated from 25 mg/day (or every other day in some cases) to 50 mg/day, adapted according to a pre-specified algorithm depending on occurrence/resolution of hyperkalaemia and/or

worsening renal function. Patients randomised to the control group will receive background therapy only. Background therapy may include any agent other than loop diuretics or potassium saving diuretics including mineral-corticoid antagonists (angiotensin converting enzyme inhibitors, angiotensin receptor blocker inhibitors, beta blockers and thiazide or thiazide-like diuretics).

2. STUDY OBJECTIVES

2.1 Primary Objective

The primary objective of the HOMAGE trial is to investigate whether spironolactone can favourably alter extra-cellular matrix remodelling, assessed by changes in the fibrosis biomarker Procollagen Type III N-Terminal Peptide (PIIINP), in patients at increased risk of developing heart failure and whether this effect is greater in patients with increased plasma concentrations of Gal-3.

The primary outcome measure is change in serum concentrations of PIIINP (RI assay, central lab) from baseline to nine months or final visit (3-6 months in patients randomized after 1st January 2018). Three to nine months is thought to be a period sufficient to influence cardiac fibrosis for which PIIINP is a widely accepted marker. Sensitivity analyses will be carried out for the primary endpoint including only patients who achieved the 9 month visit. Further sensitivity analyses will be carried using PIIINP results at the 1 month visit.

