4.3 Time-Points For Analysis

The original primary efficacy analysis requires measurement of serum levels of PIIINP at baseline and at 9 months. Patients randomised after 1 January 2018 will only achieve a maximum final visit of between 3 and 6 months. For the primary analysis, we will use

samples from the final trial visit provided the visit occurred at least 3 months after randomisation. Other visits are described in the schedule in appendix 1.

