4.7 Primary Endpoint Analysis

The analysis of the primary end-point PIIINP (change from baseline to the final visit) will be carried out using analysis of covariance (ANCOVA). A linear regression model will be fitted,

including a binary variable to indicate the treatment group (placebo/spironolactone), a binary variable to indicate the baseline Gal-3 group (below/above median) and baseline PIIINP. An interaction term will be included to evaluate the additional impact of spironolactone in the elevated Gal-3 group. Residual analysis will be used to examine the fit of the model to the assumptions of linear regression and data may be transformed to meet the assumptions of linear regression.

As this is a proof of concept trial additional exploratory analyses will be carried out for the primary outcome. In particular Gal-3 will be considered categorised into thirds i.e. cut at the tertiles of the distribution, and treated as a continuous variable. Both of these methods may provide gains in power to detect an interaction compared to treating Gal-3 as elevated or not based on the median value.

The ANCOVA model analysing change in PIIINP requires PIIINP to be available at both the baseline and final visit. If a patient is missing PIIINP at either baseline or final visit they are automatically dropped from the analysis. Sensitivity analyses will be carried out using multiple imputation with chained equations to impute missing baseline and/or final visit values.

An alternative approach to the standard ANCOVA analysis for clinical trials with a single follow-up measure of the outcome plus a baseline measure, was proposed by White and Thompson [2005]. This method includes the baseline measure as an additional outcome, constrained to have the same mean in both groups and allowed to be correlated with the follow-up measurement. In the absence of missing data this model produces identical effect estimates to the ANCOVA model and almost identical standard errors. In the presence of missing baseline data this model has the advantage of being able to include patients with a follow-up measurement of the outcome but who are missing a baseline measure. This method may therefore allow gains in statistical power in the presence of missing data.

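### The primary model pools 3-6-month and 9-month follow-up with no cohort term, and the one check on that mix is worded by visit achieved instead of by randomisation date

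*SAP*

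**What the plan says.** **Follow-up length.** SAP 1.3 gives nine months to patients randomised before the end of 2017. For the rest it says: "Patients randomised from 1 January 2018 until 30 June 2018 will be followed up for a period of between 3 and 6 months". Planned duration therefore depends on calendar date and not on arm.

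**Outcome.** SAP 2.1 defines the primary outcome as the change in PIIINP "from baseline to nine months or final visit (3-6 months in patients randomized after 1st January 2018". SAP 4.3 takes "samples from the final trial visit provided the visit occurred at least 3 months after randomisation".

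**Model.** SAP 4.7 fits a linear regression "including a binary variable to indicate the treatment group (placebo/spironolactone), a binary variable to indicate the baseline Gal-3 group (below/above median) and baseline PIIINP". It adds: "An interaction term will be included to evaluate the additional impact of spironolactone in the elevated Gal-3 group". No term represents cohort or follow-up time. A patient without PIIINP at baseline or final visit is dropped, with multiple imputation as a sensitivity analysis.

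**Check on the mix.** SAP 2.1 plans a sensitivity analysis "including only patients who achieved the 9 month visit". It also plans an analysis of 1-month PIIINP, which cannot compare 3-6 months with nine months.

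**The concern.** The short follow-up cohort arose from the recruitment timetable, so a reader will ask whether the effect at 3-6 months is the effect at nine months. The plan's only answer is the 9-month subset, and its wording may select on something that happens after randomisation.

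Take a patient in the nine-month cohort whose final trial visit falls after month 3 but before month 9. Under SAP 4.3 this patient's sample enters the primary analysis. Under an attendance reading of SAP 2.1 the patient leaves the check. The two analyses would then differ both in follow-up length and in which nine-month-cohort patients they keep. The drug is open label and its dose is adapted to potassium and renal function (SAP 1.3), so it is possible, though the SAP does not show it, that early final visits differ by arm. If the two results disagreed, the sponsor could not say whether duration or selection was the cause.

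The Gal-3 interaction could also be affected. If the treatment effect differs by cohort and the Gal-3 distribution shifts with enrolment period, part of a cohort difference would appear in the treatment-by-Gal-3 term.

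**Working it through.** **1. The plan's own power figures.** Inputs from SAP 3.2: residual SD 1.73 µg/l, two-sided 5%, 1:1 allocation, Gal-3 split at the median (four equal cells). SE = SD × √(16/N); power = Φ(δ/SE − 1.96).
- N = 800, δ = 0.79: SE = 0.2447, power 89.8% (stated 90%).
- N = 500, δ = 0.87: SE = 0.3095, power 80.3% (stated 80%).
- N = 500, δ = 1.0: power 89.8% (stated 90%).

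All three reproduce. The sample-size arithmetic is not in question.

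**2. Two uses of one verb.** SAP 4.6 reports the number and percentage of patients achieving each visit, which is attendance. SAP 4.3 says "Patients randomised after 1 January 2018 will only achieve a maximum final visit of between 3 and 6 months", which describes planned follow-up. The check in SAP 2.1 can be read either way. Only the planned-follow-up reading gives a set defined at baseline.

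**3. Dilution, for illustration.** The SAP does not give the share f of patients in the short cohort. Assume f = 10-40%, a final sample at m = 3-6 months, and linear accrual to nine months. Pooled fraction = 1 − f + f × m/9.
- f = 0.1, m = 6: 0.9 + 0.067 = 0.97.
- f = 0.4, m = 3: 0.6 + 0.133 = 0.73.

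If 0.87 is read as a 9-month interaction, the pooled value is 0.84 to 0.64 µg/l. With SE 0.3095, power is 78% to 54%. If short-cohort patients instead show 50-100% of the interaction, the pooled value is 0.70-0.87 µg/l and power is 61-80%.

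**4. Selection, for illustration.** Suppose 10% of spironolactone and 5% of control patients in the nine-month cohort miss month 9, and their PIIINP change differs by one SD from that of attenders. The attenders' treatment contrast then shifts by (0.10 − 0.05) × 1.73 = 0.09 µg/l.

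A simulation with no true effect gave a treatment bias of about −0.07 to −0.25 µg/l. It assumed 5% control and 10-20% spironolactone non-attendance, with odds of non-attendance rising 1.5-2.0 times per SD of PIIINP change on spironolactone. The interaction was biased (about −0.08 to −0.25) only when this dependence was confined to the high Gal-3 spironolactone cell. With non-attendance unrelated to PIIINP change, the bias was about zero.

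These figures compare attenders with everyone randomised into the cohort. The primary complete-case analysis carries part of the same shift. Only patients with a usable sample between month 3 and month 9 separate the two analyses.

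**5. Precision of cohort-specific estimates** (N = 500, same assumed shares).
- Nine-month cohort, N = 450 to 300: interaction SE = 1.73 × √(16/450) = 0.33 to 1.73 × √(16/300) = 0.40. Power for 0.87 is 76% to 59%.
- Short cohort, N = 50 to 200: interaction SE = 1.73 × √(16/50) = 0.98 to 1.73 × √(16/200) = 0.49.
- Treatment-by-cohort difference: SE = 1.73 × √(4/50 + 4/450) = 0.52 to 1.73 × √(4/200 + 4/300) = 0.32, so a 95% half-width of about 1.0 to 0.6 µg/l.

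**The case against.** The strongest reply has four parts.

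**The extra selection may be empty.** As Appendix 1 reads, central biobank blood is drawn only at inclusion and at the final visit, and the earlier final visit is noted only for the three-month follow-up patients. If no nine-month-cohort patient gives a final sample early, the check is simply the primary-analysis patients of that cohort. This stands as a limit. But SAP 4.3 accepts final visits from 3 months without restricting them to the short cohort, so the case is not excluded.

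**The primary analysis also conditions on attendance.** This is correct. A reader might infer that the check brings in a bias from which the primary analysis is free, or that only the check departs from a randomised comparison. The SAP does not support that: SAP 4.7 drops patients without a final value, so the check can only add to a selection already present.

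**Pooling is legitimate.** A reader might infer that leaving cohort out biases the treatment effect. It does not, because planned duration depends on date and not on arm. Nor is it true that the trial could not show dilution: setting the pooled estimate beside the 9-month estimate gives some information, and SAP 2.1 argues that three to nine months is long enough to act on fibrosis.

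**The power loss is not established.** This also stands. SAP 3.2 does not call 0.87 a 9-month effect, and the recalculation dates from March 2018, when short follow-up had begun, so it may be the target for the pooled outcome. Linear accrual from zero also sits uneasily with the rationale in SAP 2.1.

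What remains is that one phrase supports two sets of patients, and no planned analysis estimates the effect by cohort.

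**Conclusion.** The point holds as a matter of interpretation and of a badly fixed sensitivity analysis, not as a demonstrated bias. The pooled result is a valid average over an unspecified mix of durations. The check meant to examine that mix may mix duration with post-randomisation selection, while a grouping known at randomisation goes unused.

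The size is open. The dilution range of 73-97% rests on an assumed short-cohort share and linear accrual; the power range of 54-78% also requires 0.87 to be a 9-month effect. The 0.09 µg/l shift rests on assumed attendance and concerns the treatment contrast; it reaches the Gal-3 interaction only if selection differs by Gal-3 group. If attendance is unrelated to PIIINP change, or no early final samples exist, the check adds no bias. The change is worth making because it is nearly free and removes the ambiguity.

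**What to change.** - Define the 9-month sensitivity set as all patients randomised into the nine-month cohort, by randomisation date. Multiply impute missing month-9 PIIINP separately by arm, with Gal-3 in the imputation model, so that the treatment-by-Gal-3 interaction is preserved. SAP 4.7 and 4.9 already plan imputation; this ties it to the cohort.
- State the date boundary once. SAP 1.3 uses before 31 December 2017 and from 1 January 2018, which leaves 31 December unassigned; SAP 2.1 and 4.3 say after 1 January.
- Add cohort as a covariate in the primary ANCOVA. This does not undo dilution, so also report the treatment-by-cohort term and the treatment-by-Gal-3 interaction within each cohort, as exploratory estimates with confidence intervals.

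The cost is one degree of freedom for the covariate and one more for the treatment-by-cohort term in the exploratory model, plus SAP wording. It needs no data beyond the randomisation date. The cohort-specific estimates will be imprecise. A difference between cohorts may also reflect enrolment period as well as duration, so it should be read as an estimate and not as a test.

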2.2 Secondary Objectives

To investigate whether, over three to nine months, spironolactone can induce favourable changes in:

1. Serum or plasma concentrations of other biomarkers of extracellular matrix turnover: PICP (synthesis), ICTP (degradation) and Gal-3;
2. Cardiac remodelling, assessed by echocardiography, including left atrial volume, left ventricular mass and Doppler measures of right and left ventricular function (E', E/A, E/E'), tricuspid regurgitation velocity (if measurable), tricuspid annular plane systolic excursion (TAPSE) and NT-proBNP;
3. Vascular function (substudy C) assessed by pulse-wave analysis (BPLab-Germany) before and after nitrates (patients may opt out of nitrates test);
4. Exercise capacity assessed by a shuttle walk test Cardiorespiratory monitoring during and after the shuttle walk test (substudy D) using a chest band (EQUIVITAL-UK) that monitors heart rate and respiration or an auditory electrode (AUDICOR-Germany) that measures heart and respiratory sounds before and immediately after exercise.

To investigate whether, over three to nine months, other biomarkers (i.e. other than Gal-3), including markers of inflammation and markers of cardiovascular disease, are predictive of treatment response for the outcomes PIIINP, PICP and ICTP. These will be regarded as secondary, exploratory analyses and will be interpreted in light of multiple testing. Treatment response at one month will also be investigated.

To investigate whether spironolactone alters the rate of:

5. The clinical composite endpoint of development of HF or AF, non-fatal MI or stroke or CV death;
6. Worsening renal function (decline in eGFR >20%);
7. Hyperkalemia or hypokalaemia (serum potassium >5.5 or <3.5mmol/L);
8. Gynaecomastia and/or breast pain;
9. Hypotension, falls and fractures.

3. STUDY DESIGN

3.1 Study design

The HOMAGE trial follows a prospective randomized open label blinded evaluation (PROBE) parallel group design.

3.2 Sample Size

Sample size calculations determined that 800 patients were required to detect an interaction term of $0.79\mu\text{g/l}$ in PIIINP with a two sided significance level of 5% and 90% power. A residual standard deviation of PIIINP of $1.73\mu\text{g/l}$ was assumed based on results from Kosmala M et al. JACC 2011: 4:1240.

The sample size was calculated using the formula for testing interactions in analysis of variance - see Lachenbruch P, (1988) Statistics in Medicine, (7) 467-469. The interaction term represents the difference in the effect of Spironolactone on PIIINP in patients with or without an elevated Gal-3 (below/above median value).

The sample size of 800 patients will provide sufficient statistical power for exploratory analyses of the main secondary endpoints listed above. For example, the trial will have 92%-power to find significant, at the 5%-alpha error level, a difference of $15\ \mu\text{g/l}$ for PICP and 78%-power to find significant a difference of $1.1\ \text{m/s}$ for E/E' ratio.

Due to difficulty with patient recruitment updated sample size calculations were carried out in March 2018. It was determined that 500 patients would provide 80% power to detect an

interaction of $0.87\mu\text{g/l}$ in PIIINP with a two sided significance level of 5% (or 90% power to detect an interaction of $1.0\mu\text{g/l}$ in PIIINP). Gains in statistical power may be gained attained through the method of analysis, in particular through treating GAL-3 as a continuous variable and using methods for repeated measurements.

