4.6 Patient Disposition, Adherence and Follow-up

The number and percentage of patients screened, randomised and achieving each visit will be reported. Adherence to randomised treatment will be summarized. The number, percentage and type of protocol deviations and violations will be reported. The number of patients withdrawing prematurely from the study or lost to follow-up will be summarised and reported along with the reasons for withdrawal or loss to follow-up.

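### The 80%/90% power figures for 500 patients in SAP section 3.2 apply to 500 patients with both PIIINP values and make no allowance for loss, although the primary ANCOVA excludes patients lacking either value

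*SAP*

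**What the plan says.** SAP section 3.2 first gives a calculation for 800 patients, with 90% power for a treatment-by-Gal-3 interaction of 0.79 µg/l: "Sample size calculations determined that 800 patients were required to detect an interaction term of" that size. The method is given as "The sample size was calculated using the formula for testing interactions in analysis of variance", with Gal-3 split at its median. On variability, "A residual standard deviation of PIIINP of $1.73\mu\text{g/l}$ was assumed". After recruitment proved difficult, the calculation was redone in March 2018: "It was determined that 500 patients would provide 80% power to detect an" interaction of 0.87 µg/l, with the alternative of "90% power to detect an interaction of $1.0\mu\text{g/l}$ in PIIINP". Neither calculation mentions patients without usable data.

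Section 4.7 defines the primary analysis as an ANCOVA of change in PIIINP and states: "If a patient is missing PIIINP at either baseline or final visit they are automatically dropped from the analysis". Section 4.3 adds that the final-visit sample is used only if the visit took place three months or more after randomisation. Under sections 4.7 and 4.9, multiple imputation is a sensitivity analysis.

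**The concern.** The sample size section and the analysis section may be counting different patients. Section 3.2 attaches power to 500 patients without saying whether they are randomised or evaluable. Section 4.7 analyses only those with a complete pair of PIIINP values. If 500 is the number randomised, the primary analysis will contain fewer, and the stated power will not be fully delivered.

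The context points towards randomised. Section 1.3 gives about 800 as the size of the study, and section 3.2 uses the same 800 in its calculation, so study size and calculation size coincide. The 500 takes the place of that 800 because recruitment was slow.

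At stake is how a non-significant interaction will be read. The trial's size has already been reconsidered downwards, and its primary question is an interaction. Readers will judge a null result against the power the plan states.

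**Working it through.** **Inputs.** Residual SD 1.73 µg/l, two-sided 5% level, Gal-3 split at the median (section 3.2); 1:1 allocation (section 3.3); interactions of 0.79, 0.87 and 1.0 µg/l (section 3.2). The loss rate is not in the SAP, so a range is assumed, with losses spread evenly over the four treatment-by-Gal-3 cells.

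**Formula.** With N/4 patients per cell, the interaction is a difference of differences between four means. Its variance is 4 × SD²/(N/4) = 16 × SD²/N, so

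SE = 4 × SD/√N, and power ≈ Φ(interaction/SE − 1.96).

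**Step 1: reproduce the plan's figures with every patient analysed.**

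- N = 800: SE = 6.92/28.28 = 0.245. For 0.79, 0.79/0.245 = 3.23 and power is 89.8% (stated 90%).
- N = 500: SE = 6.92/22.36 = 0.309. For 0.87, 0.87/0.309 = 2.81 and power is 80.3% (stated 80%).
- N = 500, for 1.0: 1.0/0.309 = 3.23 and power is 89.8% (stated 90%).

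Solving for N at the stated powers gives 808, 498 and 504. A noncentral t calculation with N − 5 degrees of freedom agrees within 0.2 percentage points. The stated numbers therefore use the whole sample and hold no hidden margin for loss.

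**Step 2: take 500 as the number randomised and remove those without an evaluable pair.** N becomes 500 × (1 − loss). The interaction detectable with 80% power is (1.960 + 0.842) × SE.

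| Assumed loss | Evaluable N | SE | Power for 0.87 | Power for 1.0 | Detectable at 80% (µg/l) |
|---|---|---|---|---|---|
| 0% | 500 | 0.309 | 80.3% | 89.8% | 0.87 |
| 2% | 490 | 0.313 | 79.5% | 89.2% | 0.88 |
| 5% | 475 | 0.318 | 78.2% | 88.3% | 0.89 |
| 10% | 450 | 0.326 | 76.0% | 86.6% | 0.91 |
| 15% | 425 | 0.336 | 73.6% | 84.6% | 0.94 |

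**Step 3: see whether the analysis rules bring lost patients back.** Within the primary model they do not. Imputation is kept for sensitivity analysis. The alternative model in section 4.7, which treats baseline as a further outcome, is described as retaining patients who lack a baseline value, not those who lack a final one.

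**The case against.** The strongest reply is that no stated figure is wrong. Section 3.2 says 500 patients, the arithmetic is right for 500 analysed, and the SAP never labels 500 as an enrolment target. This stands, and it is why the point is conditional. A reader might infer that the plan's power is simply overstated. The SAP does not establish that, because it gives neither the meaning of 500 nor a loss rate.

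A reader might also infer that the figures hold only if nobody withdraws. That goes too far. A patient who stops treatment but gives a final sample at three months or later still counts, and a loss of 2% leaves 79.5% and 89.2%. Nor does section 4.6 predict losses. Its statement "The number of patients withdrawing prematurely from the study or lost to follow-up will be summarised" is routine disposition reporting and carries no rate.

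Three possible offsets deserve mention.

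- Section 3.2 expects gains from treating Gal-3 as continuous and from repeated-measurement methods. It quantifies neither. Section 4.7 makes continuous Gal-3 exploratory, and the primary model uses a median split and one follow-up value.
- Adjustment for baseline PIIINP could reduce the variance. If 1.73 were unadjusted, a baseline-to-outcome correlation of about 0.32 would offset a 10% loss, since 1 − 0.32² = 0.90. But the SAP already calls 1.73 a residual SD and does not say that a further reduction is available.
- In a Phase II proof-of-concept trial, a null interaction is best judged by its estimate and confidence interval. That is fair and limits the consequences, but it does not make the stated power clearer.

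**Conclusion.** The point holds in conditional form. The 80% and 90% figures are correct for 500 patients with evaluable PIIINP at both visits, and they contain no allowance for loss. The primary analysis excludes patients without such a pair. If 500 is the number randomised, which is the more natural reading, power falls short of the stated values by about 2 percentage points at 5% loss, 3 to 4 at 10%, and 5 to 6 at 15%. The detectable interaction at 80% power moves from 0.87 to between 0.89 and 0.94 µg/l.

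These sizes rest on the assumed loss range, on losses spread evenly over the four cells, and on an SD of 1.73 in the primary model. The shortfall is modest and does not call the design into question. It does affect a figure against which the primary result will be read.

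**What to change.** In section 3.2, state that 80% power for 0.87 µg/l and 90% for 1.0 µg/l apply to 500 patients with evaluable PIIINP at baseline and at a final visit that satisfies section 4.3. Add the power for 500 randomised at the proportion lacking an evaluable pair, pooled over the arms so that no comparison by treatment is made. Until that proportion is known, an illustration would do: with 10% lacking a pair, power is about 76% for 0.87 and 87% for 1.0. If 500 was always meant as the evaluable number, saying so settles the ambiguity.

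The change is to wording only. It needs no further enrolment and no change to the model or test. The one cost is a slightly less favourable stated power.
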